9.0 Statistical Considerations

This study is a non-inferiority multicenter randomized controlled double-blinded trial that evaluates the efficacy of injectable methylprednisolone acetate monotherapy and ketorolac monotherapy in the treatment of patients with subacromial impingement syndrome in the outpatient setting. Therapeutic arms consist of two groups (groups 1 and 2 receiving injectable methylprednisolone acetate and ketorolac, respectively). Patients will be evaluated and compared based on the ASES self-assessment score (ranging between 0 and

100). Our main outcome is ASES score at the 12-week time-point, with details of analysis provided in the next paragraph. We will also, as exploratory analysis, compare the functional outcome at 2 and 4 weeks post-injection. We will report summary statistics containing means and standard deviations of ASES scores for each treatment arm at each time point. We will determine whether there is non-inferiority of ketorolac at each time point.

Based on historical data (at 12 weeks post injection), the mean ASES score in the control (steroid) group is expected to be about 68.7, and the standard deviation about 12.3 [18]. The ASES patient self-assessment is a validated questionnaire that can quantify pain and decreased function of the affected shoulder, and it is usually filled out by patients as part of routine care for shoulder pain [19, 20]. Based on a review of the literature, the minimum clinically relevant effect size was determined to be ranged between 12 and 17 [21]. We therefore chose to use the lower value as reference. We calculated the minimum sample size (n) that would be required in order to ensure that the study has an 80% power with an enrollment ratio of 1, using the following formula:

$$2n = \frac{4(z_{1-\alpha} + z_{1-\beta})^2 \sigma^2}{\Delta^2} = \frac{4(1.64 + 0.84)^2 \cdot 12.3^2}{12^2} = 25.8 \approx 26$$

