In this formula, Δ represents the absolute difference between the means (μ) of groups 1 and 2 ($\Delta=|\mu_2 - \mu_1|$); σ , the variance of the mean; n, the sample size per arm; α , the probability of type 1 error (0.05); β , the probability of type II error (0.2); and z, the critical z value for a given α or β . To this end, 13 individuals per arm (26 in total) should have been enrolled and completed the trial. Assuming that 20% of patients will be lost to follow-up [3], we will attempt to enroll $26/0.8 = 33$ patients. For this end, we would aim at including a total of 40 patients in the study, which correspond to 20 patients per therapeutic arm. We will also assess whether there are differences in baseline scores between the 2 groups. In the case that the ASES scores differ, we will control for baseline value for each patient by including it as a covariate in a linear regression analysis, with covariates being baseline value and treatment group.

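### The primary week-12 comparison by default drops patients with no week-12 ASES score, although 20% loss is expected and their week-2 and week-4 scores could be used

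*Combined protocol and SAP*

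**What the plan says.** All of this is in section 9.0 (Statistical Considerations) unless noted.

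- Design and endpoint: "This study is a non-inferiority multicenter randomized controlled double-blinded trial", and "Our main outcome is ASES score at the 12-week time-point".
- Weeks 2 and 4: "We will also, as exploratory analysis, compare the functional outcome at 2 and 4 weeks post-injection". The section adds "We will report summary statistics containing means and standard deviations of ASES scores for each treatment arm at each time point" and "We will determine whether there is non-inferiority of ketorolac at each time point".
- Model: the only one named is a regression, used if baseline scores differ. It adjusts for baseline by "including it as a covariate in a linear regression analysis, with covariates being baseline value and treatment group".
- Expected loss: 20%. The sample-size paragraph says that "13 individuals per arm (26 in total) should have been enrolled and completed the trial", inflates 26 to 33, and sets a target of 40.
- Section 8.0 (Handling of Withdrawals) asks patients who withdraw voluntarily to keep attending scheduled evaluations and to complete a final one.

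The plan names no analysis set, missing-data method, repeated-measures model or sensitivity analysis.

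**The concern.** Neither stated form of the primary analysis has a term through which a week-2 or week-4 score can inform week 12. A patient with baseline, week-2 and week-4 scores but no week-12 score therefore adds nothing to the primary contrast. Enrolling more patients protects power, but it does not make those who remain representative of those randomised.

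In a non-inferiority trial, an error that shrinks a true deficit produces a false positive claim. Loss after week 4 is also plausible here. Section 6.0 (Assessment of Subject Compliance) collects weeks 2 and 4 by phone or email but places week 12 in the clinic, although section 5.0 allows a call or email at all three times. Loss after week 4 is the pattern for which the interim scores help most.

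**Working it through.** **1. The plan's own figures.** 2n = 4(1.64 + 0.84)² × 12.3² / 12² = 25.85, so 26 in total; 26/0.8 = 32.5, so 33. Both reproduce. With 40 enrolled and 20% lost, 32 remain (16 per arm). The standard error is then 12.3 × √(2/16) = 4.35, and power is Φ(12/4.35 − 1.645), about 87% (85% with the t distribution). The expected loss does not take power below 80%, so the issue is bias.

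**2. Inputs for the bias.**
- From section 9.0: 20 per arm, SD 12.3, steroid mean 68.7.
- Read from section 9.0: a margin of 12 (the plan uses 12 as Δ but does not call it a margin) and one-sided α of 0.05 (implied by z = 1.64).
- Assumed, not in the documents: true difference of -12 at weeks 4 and 12, so ketorolac mean 56.7; SD 12.3 at every visit; a common correlation ρ between visits of 0.6 (range 0.5 to 0.8); loss after week 4 with probability p_L if the week-4 score is below 58 and p_H otherwise.

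**3. Formulas.** In one arm with mean μ, let z = (58 − μ)/12.3.
- Loss: L = Φ(z)p_L + [1 − Φ(z)]p_H.
- Upward shift in the mean week-4 score of those who stay: S = 12.3 φ(z)(p_L − p_H)/(1 − L).
- Unadjusted week-12 bias towards ketorolac: ρ(S_ket − S_ster).
- False non-inferiority: about Φ(bias/SE − 1.645), with SE = 12.3 √(1/n_ket + 1/n_ster) and n the expected number remaining in each arm.

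For ketorolac z = 0.106, Φ = 0.542, φ = 0.397. For steroid z = −0.870, Φ = 0.192, φ = 0.273.

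**4. Stress case** (ketorolac 50%/5%, steroid 10%/20%).
- Ketorolac: L = 0.542 × 0.50 + 0.458 × 0.05 = 0.294; S = 12.3 × 0.397 × 0.45/0.706 = 3.11.
- Steroid: L = 0.192 × 0.10 + 0.808 × 0.20 = 0.181; S = 12.3 × 0.273 × (−0.10)/0.819 = −0.41.
- Bias: 0.6 × (3.11 + 0.41) = 2.1 points.
- SE: 12.3 × √(1/14.1 + 1/16.4) = 4.47. Rate: Φ(2.11/4.47 − 1.645) = 12%.

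**5. All scenarios at ρ = 0.6**, same formulas:

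| Loss rule (below 58 / otherwise) | Loss, ketorolac v steroid | S_ket − S_ster | Unadjusted bias | False non-inferiority |
|---|---|---|---|---|
| Common rule, 30%/10% | 21% v 14% | 1.23 − 0.78 = 0.45 | 0.3 | 5.7% |
| Ketorolac 30%/8%, steroid flat 20% | 20% v 20% | 1.34 − 0 = 1.34 | 0.8 | 7.2% |
| Stress case | 29% v 18% | 3.11 + 0.41 = 3.52 | 2.1 | 12% |
| Stress rules swapped between arms | 15% v 14% | −0.57 − 1.75 = −2.32 | −1.4 | 2.4% |

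Simulation with t bounds agrees: biases of 0.25, 0.8, 2.1 and −1.5, and rates of 5.6%, 7.1%, 11.8% to 11.9% and 2.4%. Over ρ from 0.5 to 0.8 the first two rows run from 0.5 × 0.45 = 0.2 to 0.8 × 1.34 = 1.1 points, and the stress case from 1.8 to 2.8.

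**6. Effect of the method.** With equal correlations, baseline adjustment multiplies the bias by about (1 − ρ). At ρ = 0.6 the stress case falls to 0.4 × 2.11 = 0.84 points; simulation gave 0.8 to 0.9 points and about 8%. The second row falls to 0.3 points and 6.0% in simulation, the first to about 0.1 point. Estimates that also used the interim scores were essentially unbiased.

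**7. Sensitivity to the loss rule.** A separate simulation used a logistic rule common to both arms, with 20% loss overall. Where the log-odds of loss rose by 1 per SD fall in the week-4 score, unadjusted bias was 0.6 to 1.2 points over correlations 0.5 to 0.9 (6.8% to 8.3%). Where they rose by 2, it was 1.4 to 2.4 points (9.6% to 14.6%). With no true difference and a common rule there was no bias. A likelihood estimate using the week-4 scores returned about -12 wherever the truth was -12.

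**The case against.** Four objections have force.

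- **The completer sentence concerns sample size.** A reader might infer from it that the plan declares a completer analysis. It does not. It says how many must finish for 80% power, and no section defines who is analysed. Dropping patients is the default consequence of the stated methods, not a declared policy.
- **The interim scores are used.** A reader might infer that they are thrown away. Section 9.0 plans summaries and non-inferiority assessments at weeks 2 and 4, so patients lost later contribute there. They are absent only from the week-12 contrast.
- **Loss may be limited.** Section 8.0 asks voluntary withdrawals to continue evaluations, and section 6.0 (Risks) puts the questionnaire at about four minutes. This helps after withdrawal, but not after true loss to follow-up.
- **The 12% figure comes from a chosen scenario.** It has low scorers leaving ketorolac while higher scorers leave steroid more often. Average loss is about 24% ((29 + 18)/2), above the planned 20%. Nothing in the documents supports opposite mechanisms by arm, and section 4.0 intends patients and surgeons to be blinded.

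Also, the conditional baseline adjustment already removes much of the bias when it is used, and multiple imputation from weeks 2 and 4 would be a reasonable alternative to the model proposed below. None of this supplies an analysis set or a missing-data method for the primary result.

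**Conclusion.** The point holds as a weakness in the choice of primary analysis: a better method is available from data the trial already collects. It should be changed, but it does not invalidate the design.

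With a true difference of -12, a margin of 12 and correlations of 0.5 to 0.8, unadjusted bias is about 0.3 to 1.0 points in moderate scenarios, with false non-inferiority of about 6% to 8% against 5%. It is about 2 points and about 12% in the arm-specific stress case; a steep rule common to both arms can reach a similar size. Baseline adjustment removes about half or more in most scenarios. Using the interim scores removes nearly all of it, provided loss depends only on observed scores.

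A reader might infer that the plan necessarily favours ketorolac. The documents do not support that: the sign depends on who leaves. The bias reverses if low scorers leave mainly from the steroid arm, and it vanishes if the arms are truly equal and loss is symmetric. The correlations and loss rules are assumptions, so no single figure should be read as the expected error rate.

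**What to change.** In section 9.0, make the primary analysis a repeated-measures model of ASES at weeks 2, 4 and 12, adjusted for baseline in all cases, with arm, visit and arm-by-visit terms. Include all randomised patients with any post-injection ASES, analysed as randomised. Compare the one-sided 95% lower confidence bound of the week-12 contrast (ketorolac minus steroid) with -12. Name a simpler fallback covariance in advance, in case the model does not converge with 40 patients.

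Add a sensitivity analysis that shifts missing ketorolac week-12 scores downwards in steps, for example from 0 to 12 points, and report where the conclusion changes. This covers what the model cannot: patients lost before week 2, who have no interim scores, and loss that depends on unobserved scores.

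The cost is a revised section 9.0, a slightly more complex model and a little more analysis work. No new data, visits or patients are needed.

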4.0 Treatment Assignment/Randomization

The following measures will be taken to ensure double-blinded randomization. Prior to the initiation of the study, computer-generated tables will be created in Excel to assign each patient a randomization number. This master list will be kept with a statistician and research coordinators, who do not have any patient contact. Based on his/her corresponding generated number (even or odd), the patient will be assigned to his/her therapeutic arm (methylprednisolone and ketorolac, respectively). The statistician will use an equally weighted random number generator to create these assignments. Therefore subjects will have an equal chance of being assigned to either treatment arm. Separate lists for male and female participants will also be generated to ensure equal gender participation. The statistician will then prepare an opaque envelope for each subject number. The unique subject number will be written on the visible outside surface of each envelope. The corresponding treatment arm assignment will be inside the envelope. The statistician will seal each envelope individually and send all of the envelopes to the research coordinator ([name]) prior to patient enrollment. The sealed opaque envelopes will be divided equally among the clinics and kept in locked containers in the research coordinator's office. The study staff will not have access to the envelopes. After ensuring that the patient has completed the ASES questionnaire (to establish a baseline prior to the injection), the study staff will contact [name] or [name] to provide them with the patient's first and last names as well as the MRN. The research coordinator will open one of the sequentially numbered envelopes to assign each patient the corresponding subject number (written on the outside of the envelope), and a member of the clinic staff will prepare the appropriate injection (see below) for the assigned treatment arm. The syringe will be covered with opaque tape prior to being given to the surgeon for administration. The injection will take place in a private clinic room in compliance with the Health Insurance Portability and Accountability Act (HIPAA) guidelines. The blinded surgeon will administer the injection into the subacromial space using standard bony landmarks from the posterolateral approach. The clinic staff will file the drug accountability log after preparing the injection and they will not disclose the treatment arm assignment to the patient nor the provider. This will maintain the blinding for both the patient and research surgeons. Patients' subject number will be recorded on their consent form and in their electronic medical record. Envelopes will be destroyed at the end of the study by the research coordinators. The statistician will unlock the master list only after patient enrollment and follow-up are complete, or if mandated by any regulatory body. Blinding will also be uncovered in case of a patient developing an adverse event while being followed in the trial.

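### The primary week-12 model is chosen from the baseline data by an undefined trigger; baseline ASES should be adjusted for in every case

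*Combined protocol and SAP*

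**What the plan says.** All references are to the combined protocol and SAP. Section 9.0 describes the design as follows: "This study is a non-inferiority multicenter randomized controlled double-blinded trial". On the primary analysis it states: "Our main outcome is ASES score at the 12-week time-point, with details of analysis provided in the next paragraph".

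What follows is the sample-size calculation and then two sentences on baseline. The first is: "We will also assess whether there are differences in baseline scores between the 2 groups". The second is the rule itself: "In the case that the ASES scores differ, we will control for baseline value for each patient by including it as a covariate". When the rule applies, the model is a linear regression with baseline value and treatment group as covariates.

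No test, significance level or number of points defines a difference at baseline. For the case where the scores do not differ, no test, model or confidence interval is named. Section 9.0 otherwise offers only means and standard deviations by arm and a statement that non-inferiority will be judged at each time point.

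Section 4.0 places the baseline questionnaire ahead of the opening of the envelope: "After ensuring that the patient has completed the ASES questionnaire (to establish a baseline prior to the injection". Section 6.0 likewise has the ASES completed before the injection. A baseline score is therefore planned for every randomised patient.

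**The concern.** In a randomised trial a baseline gap between arms arises by chance. Its statistical significance says little about how far it moves the outcome comparison; that depends on the size of the gap and on how strongly baseline predicts week 12. A rule that looks at the gap first and then picks the model has three possible consequences.

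- **Lost precision.** If the trigger is a test at the 5% level, about 95% of trials would be analysed without baseline, although the scores are available.
- **An open choice.** Because the trigger is not defined, two analysts can read the same sentence differently and reach opposite non-inferiority verdicts on the same data. If the reading is settled after week-12 results are known, type I error is no longer protected.
- **Carry-over in a single trial.** A chance gap below the trigger passes uncorrected into the week-12 difference.

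**Working it through.** **Inputs from section 9.0.** Week-12 SD 12.3; difference of 12 points, taken here as the non-inferiority margin; α = 0.05 with z = 1.64, hence one-sided; power 80%; 1:1 allocation; 13 completers per arm required; 40 enrolled with 20% loss, so 40 × 0.8 / 2 = 16 completers per arm expected.

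**Assumptions not in the document.** The correlation r between baseline and week-12 ASES (0.3, 0.5 and 0.7 shown here; lower values are taken up under the objection) and the trigger threshold.

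**Step 1: the plan's own figure.** 2n = 4 × (1.64 + 0.84)² × 12.3² / 12² = 25.8, rounded to 26, or 13 per arm; 26 / 0.8 = 32.5, rounded to 33. Both reproduce. The calculation uses the unadjusted SD.

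**Step 2: what adjustment offers.** Residual SD = 12.3 × √(1 − r²) = 11.73, 10.65 and 8.78 at r = 0.3, 0.5 and 0.7. With these SDs the same formula needs 12, 10 and 7 per arm for 80% power.

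**Step 3: power of the stated rule.** 200,000 simulated trials per setting; bivariate normal baseline and week-12 scores; true difference 0; t-based one-sided 0.05 tests against the 12-point margin. The rule uses a baseline t-test at p<0.05 as trigger.

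| Completers per arm | r | Rule | Always adjusted |
|---|---|---|---|
| 16 | 0.3 | 85.4% | 87.1% |
| 16 | 0.5 | 86.1% | 92.1% |
| 16 | 0.7 | 86.9% | 98.0% |
| 13 | 0.3 | 78.0% | 79.7% |
| 13 | 0.5 | 78.6% | 86.0% |
| 13 | 0.7 | 79.6% | 95.1% |

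Looser triggers shrink the loss. At r = 0.5 and 16 per arm, power is 86.7% (p<0.10), 87.7% (p<0.20) and 89.7% (p<0.50). If any numerical gap triggers adjustment, the loss is zero. Independent repeats agreed to within about 0.2 percentage points.

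**Step 4: disagreement.** With 16 per arm and no true difference, the p<0.05 rule and the always-adjusted model give different verdicts in 5.0%, 8.4% and 11.7% of trials (r = 0.3, 0.5, 0.7).

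**Step 5: type I error (true difference −12, 16 per arm).** Rule with the trigger fixed at p<0.05: 4.8%, 4.5% and 4.1%, with mean bias below 0.01 points. If the more favourable of the adjusted and unadjusted results may be reported: about 6.3%, 7.0% and 7.9%.

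**Step 6: carry-over of an undetected gap (r = 0.5, 16 per arm).** The largest non-significant gap is t(0.975, 30) × 12.3 × √(2/16) = 8.9 points, if the baseline SD is also 12.3. The shift in the week-12 difference is r × (week-12 SD / baseline SD) × gap = 0.5 × 8.88 = 4.4 points at that edge (2.7 at r = 0.3, 6.2 at r = 0.7). The baseline SD cancels from the shift. The mean shift is 1.6 points over all undetected gaps and 2.9 points over those above one standard error.

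At the margin, false non-inferiority is 7.7% when the undetected gap favours ketorolac (47.5% of trials) and 1.3% when it favours the steroid. For gaps above one standard error (about 14% of trials each way) the figures are 13.4% and 0.5%. These average back to the overall rate: 0.475 × 7.7 + 0.475 × 1.3 + 0.05 × 5 (nominal, for the 5% of trials that are adjusted) = 4.5%.

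**The case against.** The strongest reply has four parts.

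1. *The gain depends on an unknown r and is not guaranteed.* This stands as a qualification. At 16 per arm, rule against always adjusted, power is 84.9% against 84.0% at r = 0, 85.0% against 84.5% at r = 0.1, and 85.2% against 85.5% at r = 0.2. At 13 per arm and r = 0 it is 77.5% against 76.2%. Below r of about 0.2, always adjusting is neutral or costs roughly one power point. Restricting entry to severe or recalcitrant cases (section 3.0) could narrow the baseline range and lower r.

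2. *The p<0.05 trigger is not in the document.* Correct. Read literally, scores on a 0 to 100 scale will almost always differ somewhat, the regression would almost always be used, and no power would be lost. That does not rescue the rule: it shows that its effect depends entirely on a definition the plan does not give.

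3. *The rule is valid on average, and the conditional error rates apply to any unadjusted comparison.* Also correct for a fixed trigger: overall type I error stays below 5%, and the conditional rates offset each other. They describe the risk in one trial with a known direction of imbalance, not a fault in the long-run error rate.

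4. *The sample-size formula implies an unadjusted comparison as the default.* That is a reasonable inference, but it is not written down, and either model would be valid only if fixed beforehand.

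**Conclusion.** The concern holds. The primary model is not fixed in advance: adjustment is conditional, the condition is undefined, and no alternative is named. This part rests on the text alone and does not depend on r.

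The efficiency loss does depend on assumptions. With a p<0.05 trigger and 16 completers per arm it is 1.7, 6.0 and 11.1 power points at r = 0.3, 0.5 and 0.7. It is smaller with looser triggers, and nil if r is about 0.2 or lower or if any gap triggers adjustment. Type I error is safe under any one fixed trigger examined, but could reach about 6% to 8% if the model were chosen after the results were seen. The wording permits that choice; nothing suggests it is intended.

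The sample size is not in error. With 16 per arm, even the unadjusted test has about 85% power. This is a should-fix point on prespecification and efficiency, not a fatal flaw.

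**What to change.** In section 9.0, delete the condition on baseline differences and state the model outright. Suggested wording: *The primary analysis is a linear regression of week-12 ASES on treatment group and baseline ASES in all patients analysed, whatever the observed baseline difference. Non-inferiority is judged from the confidence interval for the treatment coefficient. The unadjusted difference is reported as a sensitivity result.*

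Report baseline scores by arm descriptively, with no role in choosing the model. Sex may be added as a covariate, since section 4.0 uses separate randomisation lists for men and women; that is good practice, and nothing above rests on it.

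The cost is one or two sentences and one degree of freedom. No new data are needed and the planned 40 patients are unchanged. The change should be made before any week-12 results are seen by arm.

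### Patients are allocated from separate male and female lists, but the only stated model leaves sex out: a minor mismatch of design and analysis, with a small possible loss of precision

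*Combined protocol and SAP*

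**What the plan says.** Section 4.0 (Treatment Assignment/Randomization) makes sex part of the allocation procedure: "Separate lists for male and female participants will also be generated to ensure equal gender participation". Within the lists the method is simple randomisation, with even or odd numbers deciding the arm: "The statistician will use an equally weighted random number generator to create these assignments". No blocks are described.

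Section 9.0 (Statistical Considerations) describes a non-inferiority trial and fixes the endpoint: "Our main outcome is ASES score at the 12-week time-point, with details of analysis provided in the next paragraph". The paragraph that follows contains one model, and it is conditional: "In the case that the ASES scores differ, we will control for baseline value for each patient". That model is a linear regression, "with covariates being baseline value and treatment group". If baseline scores do not differ, no test or model is named. Sex is absent from section 9.0 on either path, as covariate or as stratum, and no reason is given.

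**The concern.** The usual principle is to analyse by the groups within which patients were randomised. Here the factor that defines the lists is known for every patient and then goes unused. One interval for the week-12 difference, from about 32 completers, decides non-inferiority. If sex is related to ASES, leaving it out leaves explainable variation in the residual and widens that interval. Silence in the plan also leaves open whether sex is added or dropped once the data have been seen.

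**Working it through.** **Inputs from section 9.0.** SD 12.3; Δ = 12 in the sample-size formula, taken here as the non-inferiority margin; α = 0.05, one-sided because the formula uses z = 1.64; 80% power; 20% loss to follow-up; target 40 patients.

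**The plan's own figure.** 4 × (1.64 + 0.84)² × 12.3² / 12² = 4 × 6.1504 × 151.29 / 144 = 25.85, so 26 in total. Then 26 / 0.8 = 32.5, so 33. Both reproduce. A target of 40 less 20% leaves 32 completers, 16 per arm. Adding sex to the model does not change these numbers.

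**Assumed inputs.** The documents give no sex effect on ASES. The gaps below are assumptions, with equal numbers of men and women and the total SD held at 12.3.

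**How much sex could explain.** With a gap d and a 50:50 split, sex accounts for (d/2)² / 12.3² of the variance:
- 5 points: 6.25 / 151.29 = 4.1%
- 8 points: 16 / 151.29 = 10.6%
- 12 points: 36 / 151.29 = 23.8%

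**Chance imbalance.** Under simple allocation, chance sex imbalance moves the unadjusted difference by an SD of about d × √(0.25 × 2/16), which is 0.9 points for d = 5 and 1.4 for d = 8. The full standard error is 12.3 × √(2/16) = 4.35 and already contains this.

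**Simulation.** There were 8,000 or 20,000 trials per setting, with 32 completers. Non-inferiority was declared if the one-sided 95% lower bound lay above -12.

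*Simple allocation within lists (as written), no baseline covariate:*

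| Assumed sex gap | Power without sex | Power with sex | Change |
|---|---|---|---|
| 0 | 84.4% | 83.4% | -1.0 |
| 5 | 84.0% | 84.4% | +0.4 |
| 6 | 84.6% | 84.9% | +0.3 |
| 8 | 84.5% | 86.9% | +2.4 |
| 12 | 83.5% | 90.6% | +7.1 |

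At gaps of 0, 6 and 12 points, type I error was 4.8%, 5.1% and 4.7% without sex, and 4.9%, 5.1% and 4.9% with it.

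*Simple allocation, baseline ASES in both models (assumed correlation with week 12 of 0.5 within sex):*

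| Assumed sex gap | Power without sex | Power with sex | Change |
|---|---|---|---|
| 0 | 91.4% | 90.5% | -0.9 |
| 5, at both times | 92.1% | 91.4% | -0.7 |
| 8, at both times | 93.2% | 93.0% | -0.2 |
| 8, at week 12 only | – | – | about +2 |

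In the first three rows, type I error stayed between 4.5% and 5.4%.

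*Lists also balanced between arms (not stated in the plan), no baseline covariate:*

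| Assumed sex gap | Type I error without / with sex | Power without / with sex |
|---|---|---|
| 5 | 4.5% / 4.9% | 85.8% / 86.6% |
| 8 | 4.0% / 4.9% | 86.9% / 89.0% |
| 12 | 2.8% / 4.9% | 88.1% / 92.7% |

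A hand check of the 8-point row: the within-sex SD is √(151.29 - 16) = 11.63, and the unadjusted standard error is too large by 12.3 / 11.63 = 1.058. The effective critical value is then 1.645 × 1.058 = 1.74, which leaves about 4% in the tail.

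**The case against.** The strongest reply is that the trial, as described, is not stratified in the sense that forces adjustment. The generator gives each patient an equal chance of either arm whatever the sex, no blocks are mentioned, and the stated purpose of the lists concerns the participation of men and women, not balance between arms. On that reading the analysis without sex is valid. A second reply is that baseline ASES would carry most of any stable sex difference, so sex adds almost nothing once baseline is in the model. A third is that every sex effect used here is assumed, and that with 32 completers power exceeds the planned 80% in every setting.

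All three replies stand, and they limit the consequence. They also rule out three stronger readings that a reader might infer:

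- **That the interval is invalid or false non-inferiority is more likely.** Under the allocation described, type I error stays near 5% with or without sex.
- **That chance sex imbalance biases the estimate.** It is ordinary sampling variation, already reflected in the unadjusted standard error.
- **That the standard error is too large because the lists force balance.** This needs balance between arms within each list, which section 4.0 does not describe. Even then the error is on the conservative side.

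The replies do not remove the mismatch itself. Sex is built into allocation, the analysis is silent on it, and no reason is given.

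**Conclusion.** The point holds as a minor one. Section 9.0 should either include the factor that defines the randomisation lists or say why not. The likely effect on power is small: about -1 to +2.5 points without baseline in the model for sex gaps of 0 to 8 points, and about -1 to +2 with baseline in it. A gain near 7 points appears only without baseline and with an assumed sex gap as large as the margin itself. These figures rest on 32 completers, SD 12.3, margin 12, a 50:50 sex split and, where baseline is used, a correlation of 0.5.

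Most of the benefit of the repair comes from the other half of the same sentence. Fitting baseline in every analysis, instead of only when baseline scores differ, raised power by roughly 6 to 9 points under the assumed correlation (for example from 84.4% to 91.4% with no sex gap), and it supplies a primary model where none is now named. That gain should not be credited to sex.

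**What to change.** Replace the conditional sentence in section 9.0 with a prespecified model: week-12 ASES will be analysed by linear regression on treatment, baseline ASES and sex (the randomisation list), fitted whatever the observed baseline difference; non-inferiority will be judged on the one-sided 95% confidence bound for the adjusted treatment difference; the same covariates will be used at weeks 2 and 4. If the sponsor prefers to leave sex out, one sentence of justification would do.

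Sections 4.0 and 6.0 should also say how the sequentially numbered envelopes are kept apart by sex and whether allocation within each list is blocked, since that decides whether the analysis without sex would be exact or mildly conservative.

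The cost is a few words and one degree of freedom. Sex must already be known in order to allocate, so no new data are needed, and the sample size does not change. The downside is up to about 1 point of power if sex is unrelated to outcome.
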